#### A. Objectives

In order to examine strategies for encouraging smoking cessation in socioeconomically disadvantaged smokers, we will randomize self-identified smokers interested in our study to one of three intervention conditions: (1) Brief motivational interviewing (MI) and referral to the NJ quitline and local Tobacco Dependence Program, (2) provision of a two-week supply of nicotine replacement patch and nicotine lozenge (NRT sampling) and referral to the NJ quitline and local Tobacco Dependence Program, or (3) referral only. This randomized controlled trial will allow for a direct comparison of three brief and easy to implement treatment conditions in relation to various cigarette smoking outcomes.

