### 1.2 Research Significance (*Briefly describe the following in 500 words or less*):

A disproportionate number of individuals who use tobacco are from low socioeconomic status (Tucker-Seeley et al., 2015). By reaching smokers at socioeconomic disadvantage who may not initially be interested in seeking cessation services and prompting quit attempts in this population, we can have a positive impact on public health.

Brief motivational interviewing is a psychosocial intervention designed to promote behavioral change and recommended as part of the clinical practice guidelines for smoking cessation (Fiore, 2008), in particular for populations with low motivation to quit. This intervention assumes clients are motivated and have the ability to quit. By avoiding direct advice or convincing, the therapist carefully uses a series of techniques to illicit intrinsic motivation from the client to change. Although MI presumably is designed to affect motivation, thereby eliciting behavioral change, mechanisms research does not support this relationship and instead suggest that a therapist's ability to engage the client in 'change talk,' i.e., talk about what it would look like to engage in different behaviors, is central to a favorable outcome. Whereas meta-analytic reviews of MI indicate relatively small effect sizes, a recent meta-analytic review that examined the combined effect of brief MI (i.e., <60 minutes) found that it was significantly related to long-term cessation ( $d=.33$ ). A similar significant effect for follow-up was found that MI that was not combined with pharmacotherapy ( $d=.21$ ).

Clinical practice guidelines additionally recommend the provision of NRT to enhance smoking cessation (Fiore et al., 2008) via reduction in nicotine withdrawal. Meta-analytic reviews generally provide support for the efficacy of NRT in promoting cessation, but are somewhat mixed. More recently, combination NRT is emerging as a preferred method that provides smokers with constant nicotine replacement (e.g., via the nicotine patch) as well as relief for 'breakthrough' cravings via the addition of gum or lozenge (Carpenter et al., 2013).

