12) **Stages of Change Algorithm** (Prochaska, Velicer, DiClemente, & Fava, 1988): This three item measure is used to assess readiness for change (i.e., smoking cessation) and will be used to categorize participants into precontemplation (i.e., not thinking about quitting), contemplation (yes, within next 6 mo.), and preparation (i.e., yes, within the next 30 days). This will then be used to inform therapist provided brief motivational interviewing.

13) **Financial Strain Scale** (Pearlin, Menaghan, Lieberman, & Jullan, 1981): This 9-item measure will be used to assess participants' perceptions of financial strain. Subjective indices of financial strain, rather than using education or income as the primary indicators of socioeconomic status have the advantage of assessing perceived burden and interference. On this measure eight items are rated on a 3-point scale (1=no difficulty to 3-very great difficulty; e.g., How difficult is it to afford a home suitable for (yourself/your family?). The final item asks participants to report how much money they have left over at the end of each month.

14) **Subjective Financial Situation Scale** (Williams et al., 2016): This single item measure asks participants to describe their subjective view of their overall personal financial situation.

15) **Attitudes Toward Nicotine Replacement Therapy scale:** This measure assesses previous offering of nicotine replacement therapy (NRT), perceived advantages to NRT use, perceived side effects, and if relevant, reasons for not using NRT.

16) **Quitting Preparation and Actions Questionnaire.** This measure is used at followup only and assesses actions consistent with preparing for or making an attempt to quit smoking.

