##### **Inclusion Criteria**

Participants must be between the age of 19 and 65, must self-report being a daily smoker and provide biochemical verification of smoking status (expired breath carbon monoxide reading >5), must be at socioeconomic disadvantage, defined as receiving services at a New Brunswick, NJ based social services agency (i.e., living in New Brunswick Housing Authority-run public housing units or requesting social services from the community social service agency, "Elijah's Promise"), and must be able to speak and read English.

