##### **Exclusion Criteria**

Exclusion criteria include taking FDA approved smoking cessation or anti-psychotic medications, self-reported medical issues of potential concern to nicotine replacement users (i.e., See Table 1, e.g., unstable angina pectoris, myocardial infarction, or significant cardiac arrhythmia (including atrial fibrillation) in the past 30 days), or self-reported pending legal issues with potential to result in incarceration. Additionally, using the not pregnant form, women must state in writing that they are not pregnant or nursing, planning on becoming pregnant in the next two months, and that they are using effective birth control.

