**6.0 Research Data Protection and Reporting**

**6.1 Data Management and Confidentiality**

**A.** Success of randomization will be checked via summary statistics of baseline demographic and psychosocial characteristics. Depending on the measurement scale of each variable, we will use either  $\chi^2$  or independent samples t-tests, corrected for unequal variances if indicated. Variables found to show significant baseline differences between groups will be included as covariates. Logistic regression analyses will be conducted to examine differences in dichotomous outcomes such as abstinence (yes/no), quit attempts (yes/no), and treatment seeking (yes/no). Because this is a small, pilot study, we will report effect sizes representing each of the two active interventions (MI and NRT sampling) as compared to the control intervention (referral only).

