Official Title: Addressing Tobacco in Public Housing Residents

Identifiers: NCT03620708

Document Date: September 27, 2019

Statistical Analysis Plan

To assess for differences in outcomes between groups we will use chi-square for dichotomous outcomes and analysis of variance / analysis of covariance for continuous outcomes. We will consider covariates based on theoretical grounds (e.g., baseline cigarettes per day, baseline motivation to quit, financial disadvantage) and significant differences between groups at baseline. Significant results will be probed using Dunnett's method, whereby our comparison of interest was between the treatment conditions and control condition. We will further report effect size estimates (i.e., f for ANOVA; Cramer's V for chi-square) to help elucidate aspects of the pilot study that may be most beneficial. Data will also be examined based on the assumption of 'missing equals smoking' and carrying the last observation (i.e., baseline data) forward, as a relatively conservative means of handling data for the n=5 participants lost to follow-up. We will refer to additional analyses of imputed data as intent-to-treat (ITT) analyses.

Outcome 1: A self-described "serious" attempt to quit smoking cigarettes since the initial study appointment, measured by the "Quitting Preparation and Actions Questionnaire."

We will use chi-square analysis to examine differences in proportion of the participants randomized to receive the three intervention groups with respect to making a serious quit attempt between the initial appointment and the 1-month follow-up period.

Outcome 2: Self-reported contact with one of two treatment referrals provided at intervention since the time of the initial study appointment

We will use chi-square analysis to examine differences in proportion of the participants randomized to receive the three intervention groups with respect to seeking treatment at either the NJ QuitLine or a NJ Quitcenter (local tobacco dependence treatment clinic) between the initial appointment and the 1-month follow-up period.

Outcome 3: Self-reported cigarettes smoked per day

We will use Analysis of Covariance (ANCOVA) to examine differences in cigarettes smoked per day at the 1-month follow-up between participants randomized to the three intervention groups. Baseline cigarettes smoked per day and measures of motivation to quit will be included as covariates.

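### Outcome 1 (serious quit attempt) is tested by an unadjusted three-group chi-square, although baseline stage of change, a likely strong predictor, is collected and the protocol's logistic regression could adjust for it.

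*SAP*

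**What the plan says.** - **Outcome and analysis.** SAP, Outcome 1, compares the proportions in the three arms by chi-square "with respect to making a serious quit attempt between the initial appointment and the 1-month follow-up period". No covariate or stratum is named. The SAP's opening paragraph says covariates, including baseline motivation, will be considered, and Outcomes 3 to 5 each name a baseline motivation or readiness covariate.
- **Protocol method.** Section 6.1 A differs: "Logistic regression analyses will be conducted to examine differences in dichotomous outcomes such as abstinence (yes/no), quit attempts (yes/no), and treatment seeking (yes/no"). It adds covariates only where arms differ significantly at baseline.
- **Who can enrol.** The Objectives say "we will randomize self-identified smokers interested in our study to one of three intervention conditions". The inclusion criteria begin "Participants must be between the age of 19 and 65, must self-report being a daily smoker and provide biochemical verification of smoking status" and contain no readiness condition. The nearest exclusion is "Exclusion criteria include taking FDA approved smoking cessation or anti-psychotic medications".
- **Stage of change.** The Stages of Change Algorithm (section 1.9 B) has a category "preparation (i.e., yes, within the next 30 days"). Its stated use is "This will then be used to inform therapist provided brief motivational interviewing".
- **Follow-up.** About one month (section 1.9 A); section 4.8 B gives 30 days.
- **Randomization.** Blocks of 3, 6 and 9, not stratified by stage (section 4.3).
- **Rationale.** Section 1.2 speaks of "By reaching smokers at socioeconomic disadvantage who may not initially be interested in seeking cessation services and prompting quit attempts in this population".

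**The concern.** The preparation category and the outcome cover the same 30 days. A participant in preparation who simply does what they already intended counts as an attempt, whichever arm they are in. Baseline stage is therefore probably one of the strongest predictors of Outcome 1, yet it enters neither the allocation nor the named test, and a plain chi-square cannot carry a covariate.

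Three things are at stake. Precision is given up at about 20 per arm. A chance difference between arms in the share already preparing passes straight into the attempt rates. And the pilot exists to supply effect sizes for a larger application (section 6.1 B), while a pooled Cramer's V reflects whatever mix of stages the recruitment produced.

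**Working it through.** **1. The plan's own figure.** Section 1.5 takes N = 60, 20 per arm, a 50% attempt rate and a 95% interval of 0.38 to 0.61. The Wald interval is 0.50 ± 1.96 × √(0.25/60) = 0.373 to 0.627, and Wilson gives 0.377 to 0.623, so the printed interval is not reproduced. It also describes one overall proportion. For a difference between two arms of 20 at 50%, the half-width is 1.96 × √(2 × 0.25/20) = 0.31. Only the 50% and the 20 per arm are used below.

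**2. Assumptions.** The documents give neither the share in preparation (f) nor attempt rates by stage. Two settings are used, both with f = 0.5:
- *Strong prognosis:* 80% attempt in preparation in every arm; among the others, 20% in control and 20% (no effect) or 50% (effect) in an active arm.
- *Weak prognosis:* 70% in preparation; among the others, 30% in control and 30% or 50% in an active arm.

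Both give a control rate of 50%, matching the planning figure.

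**3. Chance imbalance.** With binomial counts in two arms of 20, the chance that the preparation shares differ by at least 20 points (4 participants) is 0.268 at f = 0.5 and 0.226 at f = 0.3 or 0.7. The SD of the difference in shares at f = 0.5 is √(2 × 0.25/20) = 0.158. Under no effect, the resulting SD of the shift in the attempt-rate difference is (0.80 − 0.20) × 0.158 = 0.095 with strong prognosis and (0.70 − 0.30) × 0.158 = 0.063 with weak. A rule that adjusts only after a significant baseline difference would usually miss this: a 20-point gap gives z = 0.20/0.158 = 1.26, below 1.96.

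**4. Precision.** Simulated variance of the stratified (Mantel-Haenszel) risk difference relative to the crude difference, two arms of 20, f = 0.5:

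| Prognosis | Active-arm effect | Variance ratio | Reduction |
|---|---|---|---|
| Strong | none | 0.66 | 34% |
| Strong | 20% to 50% outside preparation | 0.81 | 19% |
| Weak | none | 0.86 | 14% |
| Weak | 30% to 50% outside preparation | 0.93 | 7% |

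In the strong, no-effect case the SD falls from 0.158 to 0.128.

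**5. Dependence on the mix.** If preparing smokers gain nothing and the others gain 30 points, the pooled difference is (1 − f) × 30: 21 points at f = 0.3, 15 at 0.5, 9 at 0.7. If preparing smokers gain 10 points, the figure at f = 0.5 is 0.5 × 10 + 0.5 × 30 = 20.

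**6. What adjustment does not do.** In the strong setting with effect, the stratified risk difference is still 0.5 × 0 + 0.5 × 30 = 15 points. With 10 per stratum per arm, the Mantel-Haenszel odds ratio is (8×2/20 + 5×8/20)/(2×8/20 + 5×2/20) = 2.8/1.3 = 2.15. Outside preparation it is (0.5/0.5)/(0.2/0.8) = 4.0.

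**7. Size of the subgroup.** With f from 0.2 to 0.5, there are 16 down to 10 non-preparing smokers per arm. At 30% v 60%, the half-width 1.96 × √((0.21 + 0.24)/n) is 33 points at n = 16 and 42 at n = 10.

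**The case against.** A reader might infer that the trial cannot show whether the interventions prompt attempts in the smokers it means to reach. The documents do not support that. The purpose in section 1.1 is to encourage disadvantaged smokers to quit, with no limit on motivation. The sentence in section 1.2 concerns smokers who may not be seeking services, which is not the same as having no plan to quit. The stage measure expects some participants in preparation, and excluding users of cessation medication removes some smokers already acting on a plan. Randomization balances attempts that would have happened anyway in expectation, so the pooled contrast is valid for the enrolled population.

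It can also be said that the plan half covers the point, since the SAP lists baseline motivation as a possible covariate and the protocol names a model that can take one. That stands as far as it goes. The analysis actually written for Outcome 1 has no place for a covariate, and the two documents name different methods.

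Two further objections stand in full. Adjusting for stage does not recover the effect in non-preparing smokers (steps 5 and 6). And the SAP already counts 5 participants lost to follow-up, so a change of lead analysis could look data-driven.

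**Conclusion.** The point holds as one of efficiency, chance imbalance and interpretation. It is not one of bias, and it does not mean the trial fails its aim. The overlap of the two 30-day windows, the absence of a readiness criterion, the unadjusted chi-square and the mismatch with protocol section 6.1 A are all in the documents. The sizes rest on assumed shares and rates: a 20-point or larger imbalance between two arms in about 27% of trials if half are in preparation, and a variance reduction of about 7% to 34%. The amount of dilution is unknown, because the share in preparation and any gain among preparing smokers are not given. A reader might also want to rest conclusions on the non-preparing subgroup; at roughly 10 to 16 per arm it can only be descriptive. The change is worth making because it uses data already collected and a model the protocol already named.

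**What to change.** - **Lead analysis of Outcome 1.** Use the protocol's logistic regression, or a Mantel-Haenszel stratified risk difference, for each active arm versus control, adjusted for baseline stage (preparation v earlier) or baseline readiness. Name the one covariate in advance. Report effect sizes with confidence intervals. If the logistic model leads, give a risk difference beside the odds ratio, because an odds ratio conditional on stage is not comparable with an unadjusted one.
- **Supportive analysis.** Keep the three-group chi-square and Cramer's V.
- **Reconcile.** Align the SAP with protocol section 6.1 A on both the method and the covariate rule.
- **Table.** Show attempt rates by arm within the two stage groups, labelled descriptive and hypothesis-generating, so that planners of the larger trial can see the mix behind the pooled figure. Do not rest conclusions on the subgroup.
- **Record.** Date the change and state that it came after loss to follow-up was known.

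The cost is revised SAP wording, one further model and one table. No new data are needed, and stage is measured at baseline, so the same adjustment can be used in the completer and imputed analyses.

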#### **B. Dependent Variables or Outcome Measures**

Our DVs of interest are as follows: (1) pre-treatment to one-month follow-up change in (1a) motivation to quit (i.e., motivation), (1b) readiness to quit, and (1c) confidence in quitting; (2) setting a quit date (yes/no); (3) making a cessation attempt (yes/no); (4) days of self-reported abstinence, and (5) achieving initial CO verified abstinence (yes/no).

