6) **Generalized Anxiety Disorder (GAD-7)**; Spitzer et al., 2006): 7-item index is a valid and efficient tool for screening for GAD and assessing its severity in clinical practice and research.

7) **Kessler Psychological Distress Scale (K6)**; Kessler et al., 2002): This 6-item measure is a validated and brief index that is used to screen for the presence of mood and anxiety disorders.

8) **Snaith-Hamilton Pleasure Scale (SHAPS)**; Snaith et al., 1995): 14-item measure used to assess the ability to experience pleasure from typically rewarding activities. Participants rate the degree to which they believe that they would experience pleasure from hypothetical situations using a 4-point Likert type scale ranging from 0 = definitely agree to 3 = definitely disagree. The SHAPS appears to demonstrate good construct validity through its significant association with a latent dimension of anhedonia and test-retest reliability.

9) **Change Questionnaire** (Miller & Johnson, 2008): Measures ratings of importance of quitting and confidence in quitting on a 10-point Likert-type scale from 0=Definitely Not to 10 = Definitely.

10) **McArthur Scale of Subjective Social Status** (Adler & Stewart, 2007): Self-report measure of an individual's sense of social status across different SES indicators. The scale is in a pictorial format, and presents the participant with a "social ladder" and asks them to place an "X" where they feel they fall. There are two separate social ladders that are presented to the participant. One is linked to traditional

SES factors, SES Ladder, while the other is linked to social standing within a community, Community Ladder.

11) **Readiness to Quit Ladder:** Single-item measure that includes ten response options that assess motivation to quit along a continuum. Options range from 10, "I have quit smoking and I will never smoke again", to 1, "I enjoy smoking and have decided not to quit smoking for my lifetime. I have no interest in quitting". As such, higher scores on this measure indicate higher readiness to quit.

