Outcome 4: Motivation and Self-efficacy for quitting smoking measured via Importance, Confidence, & Readiness Questionnaire" (rated on a 0 to 10 scale)

We will use separate Analysis of Covariance (ANCOVA) to examine differences in a) Self-reported Importance of quitting, b) Self-reported Confidence in one's ability to quit, and c) Self-reported Readiness to quit at the 1-month follow-up between participants randomized to the three intervention groups. Baseline ratings of motivation to quit will be included as a covariates.

Outcome 5: "Readiness to Quit Ladder" (with 10 non-numbered choices reflecting varying degrees of readiness

We will use Analysis of Covariance (ANCOVA) to examine differences in cigarettes smoked per day at the 1-month follow-up between participants randomized to the three intervention groups. Baseline score on the Readiness to Quit Ladder will be included as a covariate.

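### SAP Outcome 4 does not specify each rating's own baseline as covariate; the gap is clearest for confidence, and the cost is precision and analyst discretion, not bias

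*SAP*

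**What the plan says.** The SAP heads Outcome 4 "Motivation and Self-efficacy for quitting smoking measured via Importance, Confidence, & Readiness Questionnaire", rated 0 to 10. The analysis sentence reads "We will use separate Analysis of Covariance (ANCOVA) to examine differences in a) Self-reported Importance of quitting, b) Self-reported Confidence in one's ability to quit", with readiness to quit as the third response. One covariate sentence then covers all three models: "Baseline ratings of motivation to quit will be included as a covariates". No scale is named in it.

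Elsewhere in the SAP:

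- Outcome 3 names the outcome's own baseline and adds motivation to it: "Baseline cigarettes smoked per day and measures of motivation to quit will be included as covariates".
- Outcome 5 names a specific scale: "Baseline score on the Readiness to Quit Ladder will be included as a covariate". However, the response written there is cigarettes smoked per day, so covariate and response do not match as the text stands.
- The opening paragraph allows further covariates on theoretical grounds, with an open list of examples, or where groups differ significantly at baseline.

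Protocol section 1.6 B treats the constructs as separate outcomes, each measured as change from before treatment: "1a) motivation to quit (i.e., motivation), (1b) readiness to quit, and (1c) confidence in quitting". Baseline confidence is planned twice: in the Visit 1 interview (section 1.3) and in the Change Questionnaire (section 1.9 B), which "Measures ratings of importance of quitting and confidence in quitting on a 10-point Likert-type scale".

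**The concern.** In an ANCOVA of a rating at follow-up, the baseline of the same rating is normally the most useful covariate. Read as written, the confidence model adjusts for baseline motivation, and nothing requires baseline confidence to be in it. The SAP heading and protocol section 1.6 B both separate confidence from motivation, so the covariate sentence does not obviously reach it.

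Two things are at stake.

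- **Precision.** Protocol section 6.1 B says the pilot's data will be used to estimate effect sizes for a larger grant application. With about 18 completers per arm, the width of those estimates matters.
- **Discretion.** An unnamed set of motivation ratings, applied to three models, lets the analyst choose among several covariate sets, each giving a somewhat different estimate and effect size.

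There is also a link to the protocol's definition of the outcome. With the own baseline in the model, the group contrast is the same whether the response is the follow-up score or the change score. Without it, the analysis no longer coincides with an analysis of change.

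**Working it through.** The plan states no SD, effect size, power or baseline-to-follow-up correlation for Outcome 4, so there is no figure to reproduce. The check has two parts.

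**1. Is the own baseline specified, and is it available?**

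| Rating | Covered by the covariate sentence? | Baseline collected? |
|---|---|---|
| Importance | Plausibly, as a motivation rating | Yes: Change Questionnaire |
| Confidence | Not on a plain reading, since the heading sets self-efficacy apart from motivation | Yes: Visit 1 interview and Change Questionnaire |
| Readiness | Arguably, since protocol section 1.9 B says the Readiness to Quit Ladder assesses motivation | Inferred only |

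The last entry is inferred because the questionnaire named in the SAP is not in the protocol's measures list. The SAP's plan to carry baseline data forward for participants lost to follow-up presupposes a baseline value for each rating.

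**2. What could the own baseline be worth?**

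Inputs from the documents: 60 participants, 20 per arm (protocol section 1.5); 5 lost to follow-up (SAP). If 60 were randomised, (60 − 5)/3 = 18.3 per arm complete.

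Assumptions, not in the documents: correlation with the follow-up rating of r_own for its own baseline and r_mot for the motivation covariate (the multiple correlation if several are used). r_own runs from 0.3 to 0.7, and r_mot from 0.3 to 0.7 times r_own.

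ANCOVA residual variance is proportional to 1 − r². Hence:

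- variance ratio = (1 − r_own²)/(1 − r_mot²)
- proportional fall in standard error = 1 − √(variance ratio)

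| r_own | r_mot | Variance ratio | Standard error with own baseline |
|---|---|---|---|
| 0.3 | 0.21 | 0.910/0.956 = 0.952 | 2.4% smaller |
| 0.5 | 0.25 | 0.750/0.9375 = 0.800 | 10.6% smaller |
| 0.7 | 0.21 | 0.510/0.956 = 0.534 | 27.0% smaller |
| 0.5 | 0.50 | 0.750/0.750 = 1.000 | no change |
| 0.3 | 0.40 | 0.910/0.840 = 1.083 | 4.1% larger |

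The first and third rows are the ends of the assumed range. The last two show that the gain vanishes, or reverses, if motivation predicts as well or better.

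For the middle case, with 18 per arm, two-sided 0.05, 80% power and a normal approximation, the detectable difference is (1.960 + 0.842) × √(1 − r²) × √(2/18), in SD units:

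- motivation covariate: 2.802 × 0.968 × 0.333 = 0.90 SD
- own baseline: 2.802 × 0.866 × 0.333 = 0.81 SD

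These two figures ignore the Dunnett comparison that the SAP specifies, which would raise both. The relative fall in standard error does not depend on the critical value.

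**The case against.** **The sentence may already include the own baselines.** Ratings and covariates are both plural, and the instrument is itself a set of 0 to 10 ratings. On that reading each model contains its own baseline and nothing is lost. This stands: the text is ambiguous. A reader might infer that the SAP replaces each scale's baseline with motivation, but it never says so. What can be said is that the covariate is not specified per scale.

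**Readiness is not clearly affected.** The protocol describes the Readiness to Quit Ladder as assessing motivation. This also stands, and it is why the point rests mainly on confidence.

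**Imbalance is already provided for.** The SAP and protocol section 6.1 A bring in variables that differ significantly at baseline, so it would be wrong to say that chance imbalance goes uncorrected. But the provision is limited. With 20 per arm and an assumed two-sided 0.05 level, two arms must differ by about 1.96 × √(2/20) = 0.62 SD before the test is significant. It also makes the model depend on the data. The theoretical-grounds clause permits an own baseline without requiring it.

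**Outcome 5 is a poor comparator.** True, since its stated response is cigarettes per day. Outcome 3 is the clean contrast.

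**The consequence is small.** Quit attempts, not these ratings, are the main outcome (protocol section 1.5), and the pilot has no power target. That limits the importance of the point but does not remove it, because the remedy costs almost nothing.

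**Conclusion.** The point holds as a gap in specification. Outcome 4 does not require the own baseline of each rating. For confidence, which the documents separate from motivation and measure at baseline, the plain reading leaves it out. For readiness the case is weaker and the availability of the questionnaire baseline is inferred.

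Under the assumed correlations the own baseline would make the standard error about 2% to 27% smaller, and about 11% smaller at 0.5 against 0.25. It would give no gain if motivation predicts equally well. These figures are illustrative, because the documents supply no correlations.

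Two stronger readings are tempting and are not supported. One is that the comparison is biased: randomisation keeps it valid with either covariate. The other is that a definite amount of power is lost: any such figure needs a correlation, a target difference and a multiplicity-adjusted critical value, and the documents give no correlation or target difference for this outcome.

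**What to change.** Replace the Outcome 4 covariate sentence with one stating that each of the three ANCOVAs includes the baseline score of the same rating as its response. At minimum, put baseline confidence in the confidence model. Name any additional motivation covariate by scale, and say in which models it appears. Confirm that the questionnaire's readiness rating was taken at baseline; if it was not, say which baseline measure stands in for it.

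Keeping a named motivation rating alongside the own baseline removes the risk of reversal in the last table row. Two covariates cannot explain less than either alone, and the price is one residual degree of freedom (51 to 50 with 55 analysed).

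The cost is one sentence in the SAP, with no new data for confidence. The SAP already reports the number lost to follow-up, so the clarification should be dated. If results by arm have already been seen, it should be labelled as made afterwards.

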### **1.5 Sample Size Justification**

We have a target N of 60 smokers (n=20/treatment condition). In terms of race/ethnicity, we anticipate our sample will be reflective of cigarette smokers living in the greater New Brunswick, NJ area: We expect to enroll two participants weekly in order to meet our target N. Estimating that 50% of the sample will make quit attempt during the course of the study, our main outcome of interest, this is adequate to group differences with 95% confidence (CI: 0.38, 0.61).

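### SAP Outcome 5 is the Readiness to Quit Ladder, but its model sentence analyses cigarettes per day, so the Ladder has no correct outcome-specific model

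*SAP*

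**What the plan says.** The SAP's opening paragraph assigns chi-square tests to dichotomous outcomes and ANOVA or ANCOVA to continuous ones. It then gives each of five numbered outcomes its own model text.

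- **Outcome 3** is cigarettes per day. Its ANCOVA has 1-month cigarettes per day as the dependent variable, and "Baseline cigarettes smoked per day and measures of motivation to quit will be included as covariates".
- **Outcome 4** uses an importance, confidence and readiness questionnaire rated 0 to 10, with a separate ANCOVA for each rating. The third is "c) Self-reported Readiness to quit at the 1-month follow-up between participants randomized to the three intervention groups".
- **Outcome 5** is headed as the Readiness to Quit Ladder, described as an instrument "with 10 non-numbered choices reflecting varying degrees of readiness". Its ANCOVA will "examine differences in cigarettes smoked per day at the 1-month follow-up between participants randomized to the three intervention groups. Baseline score on the Readiness"; the baseline Ladder score is the only covariate listed.

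The protocol (section 1.9 B, Online Measures) describes the Ladder as a single-item measure with its own score, on which "higher scores on this measure indicate higher readiness to quit". Section 1.6 B of the protocol lists change in readiness to quit among the dependent variables.

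**The concern.** The heading and the covariate of Outcome 5 concern the Ladder, but the dependent variable is a different endpoint that Outcome 3 already covers. An analyst who follows the sentence never analyses the Ladder score. That analyst also produces two ANCOVAs of 1-month cigarettes per day with different listed covariates, and nothing in the SAP says which one is to be reported.

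This matters because the protocol (section 6.1 B) says the pilot data will be used to estimate effect sizes for a larger grant application, and the SAP promises the effect size f for its ANOVA-type analyses. On the literal text the Ladder would yield no effect size. An analyst who instead fits the evidently intended model departs from the written plan. The SAP already reports five participants lost to follow-up, so it was written with some follow-up results in hand. An undocumented departure would be hard to tell apart from a post hoc choice.

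**Working it through.** No figure in the plan has to be reproduced. The check is a comparison of text and a count of models.

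**1. Outcomes 3 and 5 side by side**

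| | Outcome 3 | Outcome 5 |
|---|---|---|
| Heading | Cigarettes per day | Readiness to Quit Ladder |
| Method | ANCOVA | ANCOVA |
| Dependent variable | 1-month cigarettes per day | 1-month cigarettes per day |
| Listed covariates | Baseline cigarettes per day; motivation measures | Baseline Ladder score |

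The two model sentences are identical word for word; only the covariate sentences differ. In Outcome 3 the heading and the dependent variable agree. In Outcome 5 they do not, although the covariate sentence ("Baseline score on the Readiness to Quit Ladder will be included as a covariate") fits the heading.

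**2. Search for a Ladder model elsewhere**

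- SAP Outcome 4c analyses readiness, but as one of three 0 to 10 ratings from a different questionnaire.
- The SAP's opening paragraph gives a general rule for continuous outcomes and does not mention the Ladder.
- Protocol section 6.1 A names logistic regression for dichotomous outcomes and no model for continuous ones.

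No sentence makes the follow-up Ladder score a dependent variable.

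**3. Count of models, before the imputed repeats**

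- Chi-square: Outcome 1 (1) + Outcome 2 (1) = 2.
- ANCOVA: Outcome 3 (1) + Outcomes 4a, 4b and 4c (3) + Outcome 5 (1) = 5.
- Total: 2 + 5 = 7.
- Dependent variable is cigarettes per day: Outcomes 3 and 5 = 2 of 7.
- Dependent variable is the Ladder score: 0 of 7.

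So 1 of 7 models, or 1 of 5 ANCOVAs, names the wrong dependent variable.

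**The case against.** The strongest reply is that nobody would be misled. The general ANOVA/ANCOVA rule covers continuous outcomes, the Ladder is a listed outcome, and its own baseline is the stated covariate. Together these point to one sensible model: 1-month Ladder score adjusted for baseline Ladder score. This stands as a statement of intent, and it is why the gap is best described as the lack of a correct *outcome-specific* model. It does not cure the text, because the specific sentence contradicts the reading that the general rule would support.

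It can also be said that the second cigarettes-per-day model need not omit its baseline, since the opening paragraph names baseline cigarettes per day among covariates to be considered. That is fair: the point is only that Outcome 5 does not list it.

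Finally, this is a small pilot, readiness is still analysed in Outcome 4c, and the correction touches neither sample size nor the main outcome. All of that is true and limits the weight of the point. Outcome 4c does not replace the Ladder, however. It uses another instrument, and the questionnaire named there does not appear under that name in the protocol's measures list, whereas the Ladder does.

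**Conclusion.** The concern holds. Outcome 5 as written specifies the wrong dependent variable, and the Ladder score is the dependent variable in none of the seven models. The error is confined to the Ladder and to the duplicate model it creates for cigarettes per day. The protocol's sample size section identifies the main outcome ("50% of the sample will make quit attempt during the course of the study, our main outcome of interest"); it is analysed by chi-square under SAP Outcome 1 and is unaffected.

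That the clause was carried over from Outcome 3 is an inference from the identical wording. The conclusion does not depend on it: the mismatch between heading and dependent variable is there whatever its origin. This should be fixed, but it does not threaten the trial's main analysis.

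**What to change.** Replace the Outcome 5 model sentence with wording such as: *ANCOVA will compare the 1-month Readiness to Quit Ladder score across the three arms, with the baseline Ladder score as covariate.* This keeps the SAP's own method and its stated covariate, so it adds no new analytic choice.

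Add a short clause saying that cigarettes per day is analysed under Outcome 3 only, together with the imputed version that the opening paragraph provides for ("We will refer to additional analyses of imputed data as intent-to-treat (ITT) analyses"). Once the sentence is corrected this clause is largely a safeguard, but it removes any doubt about which model governs. Record the change as a dated correction.

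The cost is one sentence and one clause, with no new data and no change to sample size.
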